3 STUDY DESIGN

3.1 Overall Study Design

This is a multicenter, open-label, Phase II, randomized, controlled study to determine the efficacy, safety, and other indicators of clinical and biological activity of the combination of danvatirsen and pembrolizumab as first-line treatment for R/M HNSCC.

After providing informed consent, patients will be assessed for eligibility during the screening phase of the study. All patients must be willing and able to provide a formalin-fixed paraffin-embedded (FFPE) archival or fresh tumor sample collected during the screening period; a fresh biopsy is preferred if safe and feasible to obtain and consented to by the patient. Following the screening period, eligible patients will be randomized in a 2:1 ratio to danvatirsen + pembrolizumab or pembrolizumab monotherapy, respectively.

Patients will be stratified by CPS (CPS ≥ 1 and < 20 vs. CPS ≥ 20). An early assessment of response in patients with CPS ≥ 1 and < 20 will be performed and should the response rate in this subgroup not pass the minimum desired efficacy level, eligibility will be restricted to patients with CPS ≥ 20 .

Patients will receive treatment in 21-day cycles. Patients assigned to the pembrolizumab monotherapy arm will receive treatment until a criterion for discontinuation is met or a maximum of 24 months/34 cycles of treatment. Patients assigned to combination therapy will receive both treatments until a criterion for discontinuation is met or the patient has received a maximum of 24 months/34 cycles of pembrolizumab, after which they may remain on danvatirsen monotherapy.

As the combination of danvatirsen and pembrolizumab has not been evaluated previously, safety will be assessed on a continuous basis. A formal review of safety will be performed by the Safety Review Committee after the first 9 patients randomized have completed at least one cycle of the assigned study treatment. If accrual reaches 20 patients prior to availability of the safety results, accrual will be suspended. If the combination is deemed intolerable, further accrual will be halted.

[figure not shown]
A futility analysis will be conducted when ORR can be assessed for the first 39 patients, as described in more detail in [Section 9.2](#).

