6 DISCONTINUATION AND WITHDRAWAL CRITERIA

6.1 Discontinuation of Study Treatment

After consultation with the medical monitor, patients in the combination arm that are discontinued from one of the study treatments may remain in the study and continue to receive the other study treatment until a discontinuation criterion for the remaining treatment has been met.

Treatment with danvatirsen and pembrolizumab should be permanently discontinued for any of the following:

- Consent withdrawal
- Intolerable AE or an AE that meets the criteria for discontinuation
- Confirmed PD
 - Clinically stable patients who experience radiographic PD by RECIST v1.1 may continue to receive study treatment if patients are otherwise tolerating study treatment in the opinion of the Investigator and there are no signs of rapid, radiographic progression of disease or progression at critical anatomical sites (e.g., cord compression or tumor impinging on a major blood vessel) requiring urgent alternative interventions. Confirmatory imaging should be performed at least 4 weeks later for patients with PD who remain on study treatment. If PD is confirmed, the patient will withdraw from study treatment.
- Clinical progression, in absence of radiographic progression by RECIST v1.1, including intolerable signs or symptoms consistent with disease progression, rapidly worsening laboratory values or relevant tumor markers, rapid decline in ECOG performance status, or impingement of the tumor at critical anatomic sites requiring urgent interventions. Whenever possible, discontinuation due to clinical progression should be discussed with the Medical Monitor
- Pregnancy
- Significant patient non-compliance with the protocol or major protocol deviation
- Investigator decision
- Sponsor decision to end the study.

Patients who discontinue study treatment will complete end-of-treatment (EOT) procedures, safety follow-up, and will enter the survival follow-up phase, as specified in the SoA (Section 8.1). See [Section 7.6](#) for more information.

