7.9.6 Reporting of Adverse Events and Serious Adverse Events

Patients will be monitored for all AEs from the time the first dose of study treatment is administered through 30 days after the last dose of study treatment and 90 days after the last dose of pembrolizumab. All AEs/SAEs occurring through the reporting period (30 days after last dose of danvatirsen or 90 days after last dose of pembrolizumab, whichever is longer) or until the time the patient begins a new anticancer treatment are reported in the CRF irrespective of causality. All AEs and SAEs that occur from the signing of the ICF until the first dose of study treatment should be recorded in the eCRF only if the event was related to a study procedure.

All patients with treatment-related AEs/SAEs should be observed until resolution or stabilization of the event. Any SAE occurring after the reporting period must be promptly reported if a causal relationship to the study treatment(s) is suspected.

Elective or previously scheduled hospitalizations for pre-existing conditions that have not worsened after initiation of treatment should not be classified as SAEs. For example, an admission for a previously scheduled ventral hernia repair would not be classified as an SAE.

All AEs should be recorded individually unless, in the opinion of the Investigator, the AEs constitute components of a recognized condition, disease, or syndrome. In the latter case, the condition, disease, or syndrome should be reported rather than each individual sign or symptom. If a constellation of signs and/or symptoms cannot be medically characterized as a single diagnosis or syndrome at the time of reporting, each individual event should be recorded as an AE or SAE, as appropriate, on the relevant form(s) (SAE Report Form and/or AE form). If a diagnosis is subsequently established, it should be reported as follow-up information becomes available. If a diagnosis is determined after the reporting of the constellation of symptoms, the signs/symptoms should be updated to reflect the diagnosis.

In general, disease progression should not be reported as an AE (or an SAE) or cause of death in this study. Instead, the AEs (or SAEs) considered as complications of disease progression should be reported. However, if no specific complications of disease progression can be identified that explain the clinical observations, “disease progression” may be reported as an SAE or cause of death.

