9.6 Analysis of Safety

The analysis of safety will focus on AEs with summaries of TEAEs (i.e., AEs that start or increase in severity after the first dose of study treatment). AEs will be coded according to the latest Medical Dictionary for Regulatory Activities (MedDRA) version available at the time of database creation. The severity of AEs will be graded according to NCI CTCAE v5.0.

The number and percent of patients with any AE will be tabulated by system organ class and preferred term using MedDRA. AEs related to danvatirsen, AEs related to pembrolizumab, all SAEs, related SAEs, and AEs by maximum CTCAE grade will be summarized similarly.

Laboratory test results after the first dose of study treatment will be summarized by shift in CTCAE grade for laboratory parameters that can be graded. Laboratory parameters that cannot be graded by CTCAE will be summarized by shifts to low, normal, or high postbaseline.

Vital signs will be summarized by the change from baseline at each postbaseline timepoint. Descriptive statistics will be provided by study visit for physical examination, ECOG performance status, ECG, and weight parameters.

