### 5.4 Reporting Conventions

All CDISC submission datasets, data listings, summaries, figures, and statistical analyses will be generated using SAS version 9.4 or higher.

Summaries will be presented by treatment arm and a cumulative overall column. Treatment arm labels will be displayed as follows.

Danvatirsen + Pembrolizumab (N=XX)	Pembrolizumab (N=XX)	Overall (N=XX)
---------------------------------------	-------------------------	-------------------

Danvatirsen + Pembrolizumab = Danvatirsen 2 mg/kg or 3 mg/kg + Pembrolizumab 200 mg IV  
Pembrolizumab = Pembrolizumab 200 mg IV

Table summaries will present patient by either planned or actual treatment assignment, as specified in the Statistical Analysis Plan. In the rare case that a subject is mis-randomized or administered the incorrect treatment, actual treatment assignment is defined as the treatment the patient received for the majority of the study.

Unless otherwise stated, listings will be sorted in the following order: Treatment arm, Subject ID, Start Date, End Date, and Parameter.

Continuous variables will be summarized by the number of non-missing observations, mean, median, standard deviation, and minimum and maximum. Summaries of change from Baseline values will only include patients with a values at both baseline and the post-baseline time-point.

Categorical variables will be summarized by presenting the frequency and percent. Percentages will be based on the number of patients in the column header unless otherwise specified in the footnote. For each variable, all categories will be shown. Zero frequencies (but not the percent) within a category will be presented.

QMD Ref: Worldwide-TMP-ST-054-1.0_Effective: 12Aug2022	Governing QMD: Worldwide-SOP-ST-026
Confidentiality Statement	
This document is the property of Worldwide Clinical Trials Inc. and may not be duplicated, copied, altered or removed from company without prior approval from Worldwide Quality Assurance or in compliance with Worldwide Standard Operating Procedures.	

Worldwide Clinical Trials Controlled Quality Management Document		
 WORLDWIDE CLINICAL TRIALS	Sponsor:	Flamingo Therapeutics
	Protocol Number:	FLM-6774-201
STATISTICAL ANALYSIS PLAN		

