### 5.13.1 Adverse Events

Treatment-emergent adverse events (TEAE) are reported according to protocol as any AE that has an onset on or after the first dose of study drug or any pre-existing condition that has worsened on or after the first dose of study drug up to the subject completion of the study.

A treatment-related AE is defined as an AE as being definitely, possibly, or probably, related to the study drug.

All TEAE summaries will include the number and percentage of subjects experiencing each adverse events as well as the total number of events. The following TEAEs will be summarized separately by system organ class and preferred term, as coded by MedDRA dictionary.

- Any TEAE
- Any TEAE (PT only)
- Related to Any Study Treatment
- Related to Danvatirsen
- Serious
- Serious Related to Any Study Drug
- Leading to Discontinuation of All Study Drugs
- Leading to Discontinuation of Danvatirsen only
- Leading to Discontinuation of Pembrolizumab only
- Leading to Dose Delays or Reductions of Any Study Drug
- Leading to Dose Delays or Reductions of Danvatirsen
- Leading to Death
- Leading to Death Related to Any Study Drug
- Toxicity Grade 3 or Higher
- By Maximum Toxicity Grade

An overall TEAE summary table will be provided separately, tabulating the number of subjects and events for any adverse event for the above categories. The following summaries will also be provided.

- Listing of Serious TEAEs
- Listing AEs Leading of Deaths
- TEAE by Preferred Term
- TEAE Related to Any Study Drug by Preferred Term

QMD Ref: Worldwide-TMP-ST-054-1.0_Effective: 12Aug2022	Governing QMD: Worldwide-SOP-ST-026
Confidentiality Statement	

This document is the property of Worldwide Clinical Trials Inc. and may not be duplicated, copied, altered or removed from company without prior approval from Worldwide Quality Assurance or in compliance with Worldwide Standard Operating Procedures.

Worldwide Clinical Trials Controlled Quality Management Document		
 WORLDWIDE CLINICAL TRIALS	Sponsor:	Flamingo Therapeutics
	Protocol Number:	FLM-6774-201
STATISTICAL ANALYSIS PLAN		

All adverse events will be listed. Listings of AEs leading to death will include a flag for on-treatment deaths. An on-treatment death is defined as death occurring from date of first dose of any study drug to 30 days after last dose of Danvatirsen or 90 days after last dose of Pembrolizumab, whichever is later.

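### TEAE tables give crude percentages and unadjusted event counts although AE collection follows time on treatment, so unequal treatment duration would distort the between-arm safety picture in either direction

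*SAP*

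**What the plan says.** The AE summaries are counts and percentages. SAP 5.13.1: "All TEAE summaries will include the number and percentage of subjects experiencing each adverse events as well as the total number of events". Protocol 9.6 is similar: "The number and percent of patients with any AE will be tabulated by system organ class and preferred term using MedDRA". The arms stand side by side; SAP 5.4: "Summaries will be presented by treatment arm and a cumulative overall column". The table list in SAP Section 11 contains no AE rate per unit of time, time-to-first-event table or fixed-window table. SAP 5.11 tabulates treatment duration, but separately and never as a denominator for AEs.

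AE collection follows treatment. Protocol 7.9.6 sets the end of the reporting period at "30 days after last dose of danvatirsen or 90 days after last dose of pembrolizumab, whichever is longer". Starting another cancer therapy closes it sooner. Treatment itself continues until confirmed progression or another stopping criterion (protocol 6.1).

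Two provisions apply to the combination arm only. A patient "discontinued from one of the study treatments may remain in the study and continue to receive the other study treatment" (protocol 6.1, after consultation with the medical monitor). After the 24-month pembrolizumab maximum, patients reach a stage "after which they may remain on danvatirsen monotherapy" (protocol 3.1).

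SAP 5.13.1 uses a different end point for TEAEs: the patient's completion of the study. The same SAP section uses the 30/90-day limits when it defines an on-treatment death.

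**The concern.** A crude percentage over a window of variable length mixes two things: how often events occur per week, and for how many weeks the patient was observed. If one arm is observed for longer, its percentage rises at an identical event rate. The total number of events does not help, because it is not divided by patient-time and also scales with the 2:1 allocation.

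Safety and tolerability is a secondary objective, and these tables are its main AE evidence. If the combination delays progression, part of an apparent excess of AEs would reflect longer observation. If the combination is stopped early, for example for toxicity, the same tables would hide part of a real excess.

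**Working it through.** **1. The plan's own figure.** The documents give no AE rate, no expected treatment duration by arm and no safety power. The one design figure used here is ORR 15% v 43%. Exact binomial enumeration of the protocol Table 9 boundaries (13/26 at the interim, 27/54 at the end) gives power 82.6% (Table 10: 82.7%) and type I error 4.5% (Table 10: 4.6%). The design figure is not in dispute.

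**2. Inputs.**
- From the documents: ORR 15% v 43%; the 42-week duration of response in the earlier danvatirsen plus durvalumab study (protocol 1.1.2), treated as a median and applied to responders in both arms; the 24-month pembrolizumab cap (104.4 weeks), applied here to both arms; the 90-day tail.
- Assumed: response starts at 9 weeks; non-responders stay 6 weeks plus an exponential time, with mean 9, 12 or 18 weeks in all; new therapy starts a mean of 4 weeks after stopping (exponential); the AE hazard h is constant and equal in the two arms.

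**3. Formula.** Window W = treatment time + min(90 days, time to new therapy). Crude incidence = 1 - E[exp(-hW)].

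**4. Worked case: non-responder mean 12 weeks, h = 0.01 per week.**
- Mean capped treatment time in responders is 57.0 weeks and the mean tail is 3.8 weeks.
- Mean window, control: 0.15 x 57.0 + 0.85 x 12 + 3.8 = 22.6 weeks. Combination: 0.43 x 57.0 + 0.57 x 12 + 3.8 = 35.2 weeks.
- E[exp(-hT)] is 0.597 in responders and 0.888 in non-responders; the tail factor is 0.963.
- Control: 1 - (0.15 x 0.597 + 0.85 x 0.888) x 0.963 = 18.7%. Combination: 1 - (0.43 x 0.597 + 0.57 x 0.888) x 0.963 = 26.5%. The ratio is 1.42 with no true difference.

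**5. Results at 15% v 43%** (control % v combination %, spurious risk ratio in brackets).

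| Events | Non-responder mean 9 wk | 12 wk | 18 wk |
|---|---|---|---|
| 0.01/week | 16.5 v 25.1 (1.52) | 18.7 v 26.5 (1.42) | 22.6 v 29.1 (1.29) |
| 0.03/week | 37.9 v 50.2 (1.32) | 42.4 v 53.2 (1.25) | 49.5 v 57.9 (1.17) |
| 0.1/week | 73.6 v 81.0 (1.10) | 78.5 v 84.2 (1.07) | 84.2 v 88.0 (1.05) |
| 0.03/week, first 12 weeks only | 27.7 v 28.5 (1.03) | 28.7 v 29.2 (1.02) | 29.3 v 29.6 (1.01) |
| 0.01/week, treatment capped at 39 weeks | 14.7 v 19.8 (1.35) | 16.8 v 21.2 (1.26) | 20.4 v 23.6 (1.16) |

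Mean windows without the 39-week cap are 20-28 v 33-39 weeks. With the ORRs that protocol Section 1.1 cites for CPS ≥1 (19% v 31-37%), the ratio at 0.01 per week is 1.12-1.31. At 15% v 15% it is 1.00.

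**6. Which way the distortion goes.** A second model takes exponential time on treatment, control median 3-6 months (assumed), h = 0.05 per month and a tail of 0 or 3 months. Combination minus control, by hazard ratio for stopping treatment:
- 0.6: +7.4 to +12.1 points
- 0.8: +3.0 to +5.5 points
- 1.0: 0 to +0.5 points
- 1.25 (combination stopped earlier): -2.6 to -3.8 points

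**7. Danvatirsen continuation.** If both drugs stop together, the 90-day pembrolizumab tail governs in both arms. Danvatirsen extends the window only when it runs more than 90 - 30 = 60 days past the last pembrolizumab dose. With ORR 15% in both arms, so that only the absence of a danvatirsen limit after 24 months differs, the excess is at most about 0.6 points. Continuing danvatirsen after an earlier pembrolizumab stop is not modelled, because the documents give no frequency for it.

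**8. Check of the remedy.** At h = 0.05 per month, non-responder median 3 months and a 3-month tail, crude incidence is 32.5% v 39.4% (a spurious 6.9 points). First events per 100 patient-months at risk are 5 in both arms.

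**The case against.** A reader might infer that the AE window does stay open longer in the combination arm, so that this arm will look more toxic. The documents do not support that. They give no expected treatment duration by arm, and step 6 shows that the sign depends on it. Nor do the danvatirsen continuation provisions carry the argument: what could be quantified is at most about 0.6 points, and early termination (SAP Section 9) leaves fewer patients able to reach 24 months.

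Other points on that side are fair:
- The safety objective is to characterise the combination, without the comparative wording used for efficacy, and no between-arm AE test is planned. Readers will still compare adjacent columns.
- Exposure is tabulated, and laboratory values are summarised by visit with spider plots for AST, ALT, hemoglobin, neutrophils and platelets, which cover danvatirsen's main named risks. Neither puts the AE percentages on a common time base.
- The risk ratio shrinks for common events and almost vanishes for early ones.
- Precision is low. With 54 v 27 patients and incidence near 35%, the 95% half-width of a difference is 1.96 x sqrt(0.35 x 0.65 x (1/54 + 1/27)) = 22 points, against a central distortion of 6.9. Sampling noise does not remove a systematic distortion, but it limits how much weight any AE contrast can bear.

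**Conclusion.** The point holds conditionally. The plan has no AE summary that accounts for time at risk, while collection follows time on treatment. The crude figures overstate the combination's relative toxicity if its treatment lasts longer, understate it if treatment is shorter, and are barely affected if durations are equal. Under the design alternative the spurious risk ratio is about 1.29-1.52 at 0.01 per week, 1.17-1.32 at 0.03 and 1.05-1.10 at 0.1, and 1.01-1.03 for events confined to the first 12 weeks. It falls to 1.16-1.35 at 0.01 per week if treatment is capped at 39 weeks.

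These sizes rest on assumed non-responder duration, time to new therapy, hazard level and constant hazard, and on a 42-week response duration borrowed from another combination. Delayed progression drives the effect. The primary analysis is untouched; what is at stake is the reading of descriptive safety tables.

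**What to change.** 1. Align the TEAE end date in SAP 5.13.1 with the protocol 7.9.6 window, so that events and time at risk use the same window. State how late SAEs suspected to be related, which protocol 7.9.6 still requires to be reported, are shown.
2. In SAP 5.13.1, for the overall, serious, Grade ≥3 and related-to-any-study-drug TEAE tables, add by arm the patients with a first event per 100 patient-months at risk. Time at risk runs from first dose to first event or the end of the window.
3. In the same tables add incidence in a common early window, for example the first 4 cycles (4 x 21 = 84 days, or 12 weeks), before Day 8 and Day 15 contacts in the control arm may move to telephone.
4. Keep the crude percentages, and state that between-arm differences are read alongside the new rows.

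The cost is SAP wording and a few table rows or columns from dates already collected. The rates assume a roughly constant hazard, which is why the common-window rows accompany them. Neither addition fully removes ascertainment differences: Cycle 1 Day 3 and Day 5 visits occur only in the combination arm, and telephone contacts from Cycle 5 only in the control arm.

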5.4 Dose Modification Guidelines and Toxicity Management

5.4.1 Purpose and Approach

If a patient experiences a clinically significant and/or unacceptable toxicity with the study treatment, dosing will be interrupted or the dose reduced. Supportive therapy will be administered as required.

If the toxicity resolves or improves to at least Grade 1 or pretreatment baseline (refer to specific toxicity criteria in [Section 5.4.2](#) for danvatirsen and [Section 5.4.3](#) for pembrolizumab) by day 21 for danvatirsen and day 42 for pembrolizumab, dosing may resume.

If the toxicity does not resolve (refer to specific toxicity criteria in [Section 5.4.2](#) for danvatirsen and [Section 5.4.3](#) for pembrolizumab) or at least improve after 21 days for danvatirsen or 42 days for pembrolizumab, dosing may still be resumed after discussion and agreement with the medical monitor.

Dose modification should only be applied if the toxicity is **at least possibly related** to study treatment and in the absence of alternative etiologies.

- When more than one toxicity is noted simultaneously with different grades of severity, the **highest grade** should be used to guide dose modification decisions.
- As one arm of this study is a combination regimen and some side effects of danvatirsen and pembrolizumab can be overlapping (e.g., possible ALT/AST elevations, thrombocytopenia, and neutropenia), every effort should be made to **attribute the toxicity to the component part** of the study treatment regimen, and **only the dose of the component part should be modified**. If the Investigator has any questions with regard to such an AE, the Investigator should immediately contact the Medical Monitor.
- In the absence of clear alternative etiology, all events of an inflammatory nature should be considered immune related.
- The reasons for dose modifications, actions taken, and outcomes will be recorded.
- For concomitant medications, dose modifications will be at the discretion of the Investigator in accordance with the severity of the toxicity.
- For temporary delays in study treatment due to toxicity, the **cycle structure** should **remain** and not be regarded as delayed. Following the resolution of toxicity, the treatment regimen will resume as previously scheduled. This plan will potentially result in skipped doses and is intended to keep the treatment cycles synchronized with study assessments.

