7.9.4 Relationship of Adverse Events to Study Treatment

For each AE/SAE, a causality assessment must be provided by the Investigator. The Investigator will use clinical judgment to determine whether or not an AE/SAE was related to each study treatment, as outlined below.

Related is defined as one of the following:

- **Definitely related:** This applies when, after careful medical consideration, there is almost no consideration of other causation.
- **Probably related:** There is a clinically plausible time sequence between onset of the AE and study treatment administration. The AE is unlikely to be caused by a concurrent or underlying illness, other drugs, or procedures. If applicable, the AE follows a clinically consistent resolution pattern upon withdrawal of study treatment.
- **Possibly related:** There is a clinically plausible time sequence between onset of the AE and study treatment administration, but the AE could also have been caused by the concurrent or underlying illness, other drugs, or procedures. Information regarding study treatment withdrawal may be lacking or unclear. “Possible” should be used when study treatment administration is one of several biologically plausible causes of the AE.

Not Related is defined as one of the following:

- **Unlikely related:** The AE is most likely due to a cause not related to study treatment administration. However, association with the study treatment cannot be completely ruled out.
- **Unrelated:** Another cause of the AE is most plausible, and a clinically plausible temporal sequence is inconsistent with the onset of the AE and study treatment administration and/or a causal relationship is considered biologically implausible.

For the purpose of regulatory reporting requirements, causal relationships of definite, probable, and possible will be considered treatment-related, while unlikely and unrelated will be considered not treatment-related.

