## STATISTICAL ANALYSIS PLAN

14.2.2.3.7	OS by Region	Stat IP	
14.3.1.1.1	Overall Treatment-Emergent Adverse Events	IP	X
14.3.1.2.1	TEAE by SOC and PT	IP	X
14.3.1.2.1.1	TEAE by PT	IP	X
14.3.1.2.2	TEAE by SOC and PT - Related to Any Study Drug	IP	X
14.3.1.2.3	TEAE by SOC and PT - Related to Danvatirsen	IP	X
14.3.1.2.4	TEAE by SOC and PT - Serious	IP	X
14.3.1.2.5	TEAE by SOC and PT - Serious and Related to Any Study Drug	IP	
14.3.1.3.1	TEAE by PT	IP	
14.3.1.3.2	TEAE by PT - Related to Any Study Drug	IP	
14.3.1.4.1	TEAE by SOC and PT - Leading to Discontinuation of All Study Drugs	IP	
14.3.1.4.2	TEAE by SOC and PT - Leading to Discontinuation of Danvatirsen	IP	
14.3.1.4.3	TEAE by SOC and PT - Leading to Discontinuation of Pembrolizumab	IP	
14.3.1.4.4	TEAE by SOC and PT - Leading to Dose Delays or Reductions of Any Study Drug	IP	
14.3.1.4.5	TEAE by SOC and PT - Leading to Dose Delays or Reductions of Danvatirsen	IP	
14.3.1.4.6	TEAE by SOC and PT - Leading to Dose Delays of Pembrolizumab	IP	
14.3.1.4.7	TEAE by SOC and PT - Leading to Death	IP	
14.3.1.4.8	TEAE by SOC and PT - Leading to Death and Related to Any Study Drug	IP	
14.3.1.5.1	TEAE by SOC and PT - Grade 3 or Higher	IP	
14.3.1.5.2	TEAE by SOC, PT, and Maximum Toxicity Grade	IP	X
14.3.2.1	Listing of Deaths	IP	X
14.3.2.2	Listing of Serious AE	IP	
14.3.4.1	Listing of Lab Abnormalities	IP	
14.3.5.1	Hematology	IP	X
14.3.5.2	Hematology Shift	IP	X
14.3.5.3	Chemistry	IP	
14.3.5.4	Chemistry Shift	IP	X (ALT/AST Only)
14.3.5.5	Coagulation	IP	
14.3.5.6	Coagulation Shift	IP	
14.3.6.1	Extent of Exposure to Danvatirsen	IP	X
14.3.6.2	Extent of Exposure to Pembrolizumab	IP	X
14.3.7.1	Vital Signs	IP	
14.3.7.2	12-Lead ECG	IP	
14.3.7.3	12-Lead ECG Shift	IP	
14.3.7.4	12-Lead ECG Abnormalities	IP	
14.3.7.5	ECOG	IP	
14.3.7.6	Post-Treatment Anticancer Therapy	IP	
Figures			
14.2.3.1.1	Duration of Treatment Swimmer's Plot	IP	X
14.2.3.2.1	Waterfall Plot - Max Percent CFB in Tumor Size	IP	
14.2.3.3.1	Spider Plot - Sum of Target Lesions vs Time by CPS	IP	
14.2.3.4.1	Forest Plot - ORR and DCR	IP	
14.2.3.4.2	Forest Plot - PFS	IP	
14.2.3.4.3	Forest Plot - OS	IP	
14.2.3.5.1	Kaplan-Meier Plot - DOR	IP	
14.2.3.5.2	Kaplan-Meier Plot - DOR by CPS	IP	
14.2.3.5.3	Kaplan-Meier Plot - PFS	IP	X
14.2.3.5.4	Kaplan-Meier Plot - PFS by CPS	IP	X
14.2.3.5.5	Kaplan-Meier Plot - OS	IP	
14.2.3.5.6	Kaplan-Meier Plot - OS by CPS	IP	
14.3.1.1	Spider Plot - AST	IP	X

QMD Ref: Worldwide-TMP-ST-054-1.0\_Effective: 12Aug2022

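### The SAP omits the protocol's summary of adverse events related to pembrolizumab and does not record the omission, so the planned tables only bound those events in the combination arm

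*SAP*

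**What the plan says.** Protocol 9.6 plans a tabulation of adverse events by system organ class and preferred term, and then adds: "AEs related to danvatirsen, AEs related to pembrolizumab, all SAEs, related SAEs, and AEs by maximum CTCAE grade will be summarized similarly". The data for both drugs will exist. Protocol 7.9.4 has the Investigator decide "whether or not an AE/SAE was related to each study treatment", and Protocol 7.9.6 repeats that causality is evaluated for each study treatment. Protocol 5.4.1 warns that "some side effects of danvatirsen and pembrolizumab can be overlapping" and tells sites to try to attribute a toxicity to one component.

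SAP 5.13.1 opens its list of outputs with "The following TEAEs will be summarized separately by system organ class and preferred term, as coded by MedDRA dictionary". Its two general relatedness entries are "Related to Any Study Treatment" and "Related to Danvatirsen". Its serious-related and fatal-related entries also refer to any study drug. The list in SAP section 11 follows the same pattern: tables 14.3.1.2.2, 14.3.1.2.5, 14.3.1.3.2 and 14.3.1.4.8 concern any study drug, and 14.3.1.2.3 is "TEAE by SOC and PT - Related to Danvatirsen". SAP section 9, which is reserved for departures from the protocol analysis, names only the early timing of the final analysis.

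**The concern.** The protocol promises an attribution summary for each drug, and the SAP delivers it for one. Programming from the SAP as written would leave a planned safety analysis unproduced, with no note to alert the author of the study report.

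The missing half has a use. Protocol 3.1 says the combination has not been evaluated before, Protocol 1.3 calls its tolerability unknown, and safety is the first secondary objective listed. Pembrolizumab is the only study drug given in both arms, so it is the only drug for which an attributed event rate can be set side by side by arm. The danvatirsen-related table is empty in the control arm by construction. The any-drug table refers to one drug in control and to two in the combination arm.

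**Working it through.** No stated figure needs reproducing. The check is a comparison of lists, followed by a bound.

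**1. Protocol 9.6 against the SAP**

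| Protocol 9.6 item | SAP 5.13.1 | SAP section 11 |
|---|---|---|
| Related to danvatirsen | Yes | 14.3.1.2.3 |
| Related to pembrolizumab | No | None |
| All serious events | Yes | 14.3.1.2.4 |
| Related serious events | Yes, any study drug | 14.3.1.2.5 |
| By maximum grade | Yes | 14.3.1.5.2 |

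SAP 5.13.1 has 15 categories and section 11 has 19 TEAE tables, from 14.3.1.1.1 to 14.3.1.5.2. The count for pembrolizumab-related events is 0 of 15 and 0 of 19.

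**2. What the two planned relatedness tables imply**

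Take an event to be related to any study drug if it is related to at least one of the two. For the combination arm, overall or in any one row, let

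- A = patients with an event related to any study drug (14.3.1.2.2)
- D = patients with an event related to danvatirsen (14.3.1.2.3)
- P = patients with an event related to pembrolizumab (no table)

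A counts the patients who fall in D, in P or in both. Hence

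A − D ≤ P ≤ A.

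The lower limit applies when no patient has both kinds of event. The upper limit applies when every patient counted in D is also counted in P. The width of the interval is A − (A − D) = D.

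**3. What this means by arm**

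- Control: no danvatirsen is given, so D = 0 and P = A. The pembrolizumab-related count is known exactly.
- Combination: P is known exactly only in rows where D = 0. In every other row it is uncertain by D patients.

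The gap is therefore likely to be widest for the toxicities the drugs share. Protocol 5.4.1 gives ALT/AST elevations, thrombocytopenia and neutropenia as examples. Those are the rows where a by-arm comparison of attributed events would most need P.

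**4. Is the omission recorded?**

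It is not in SAP section 9. The opening of Protocol section 9 requires changes to the analyses to be described and justified in the study report, so recording it there is still possible.

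**The case against.** The strongest reply is that the effect of adding danvatirsen does not depend on attribution. Both arms receive pembrolizumab, and the SAP plans by-arm tables of all TEAEs and of serious, grade 3 or higher, maximum-grade and fatal ones. It also plans "TEAE by SOC and PT - Leading to Discontinuation of Pembrolizumab" and a matching table for pembrolizumab dose delays. This stands. A reader might infer that no planned table can show whether danvatirsen worsens toxicity on pembrolizumab, but these tables bear directly on that question. One caution applies: SAP 5.13.1 words the discontinuation category as pembrolizumab only. In control, stopping pembrolizumab is stopping all study drug, so that row may not mean the same in both arms.

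Second, attribution in an open-label trial is a judgement. The investigator has one drug to blame in control and two in the combination arm, so an identical event may be assigned differently. This also stands. The missing table would be descriptive, not a clean comparison of like with like.

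Third, the pembrolizumab-related rate might be recovered. If attributions to the two drugs were independent, with a and d the proportions behind A and D, then p = 1 − (1 − a)/(1 − d). Nothing in the documents supports independence, and the overlap described in Protocol 5.4.1 argues against relying on it. Without it, only the bound remains.

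Fourth, the SAP lists may be incomplete. Table 14.3.1.4.6 is in section 11 but not among the 5.13.1 categories, and section 11 refers to a shell document for final titles and numbers. The shells may already hold the table, but the plan does not show it. All adverse events are listed in 16.2.7.1 and causality is collected per drug, so no data are lost.

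**Conclusion.** The mismatch is certain: a summary promised in Protocol 9.6 is missing from SAP 5.13.1 and from the table list, and SAP section 9 is silent on it. The consequence is limited. Investigator-attributed pembrolizumab events in the combination arm can be bounded only to within D patients, so they cannot be compared by arm except in rows with no danvatirsen-related events. No endpoint test or decision rule is touched, and the comparison of toxicity regardless of attribution is intact.

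A reader might also infer that Protocol 9.6 requires serious or maximum-grade tables for each drug. It does not. It asks for related serious events without splitting them by drug, which 14.3.1.2.5 meets, and it does not cross relatedness with grade.

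The bound assumes that relatedness to any study drug means relatedness to at least one of the two. The conclusion also assumes that the table shells, which are not available here, do not already include the summary.

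**What to change.** Make three additions:

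- a category for TEAEs related to pembrolizumab in the SAP 5.13.1 list;
- one table by arm, system organ class and preferred term, placed beside 14.3.1.2.3;
- one row in the overall TEAE summary, 14.3.1.1.1.

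If the sponsor prefers not to produce the summary, SAP section 9 should say so and give the reason, and the study report should repeat it.

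The cost is one repeat of an existing table with a different causality flag, and no new data. SAP section 5 requires the plan and shells to be approved before database lock. After lock, the same change would go into the addendum described there.
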